### **7.1.1 For Disease Characteristics**

For baseline disease characteristics (eg, age at end date of index trauma, time since end date of index trauma), if month and day are missing, July 1 will be imputed; if only the day is missing, the 15th will be imputed.

## **7.2 Safety Analysis**

Unless specified below, safety analyses will be based on the observed data.

### **7.2.1 For Adverse Events Onset Dates**

If onset date is completely missing, onset date is set to the first dose.

If (year is present and month and day are missing) or (year and day are present and month is missing):

- If year = year of the first dose, then set month and day to month and day of the first dose
- If year < year of the first dose, then set month and day to December 31.
- If year > year of the first dose, then set month and day to January 1.

If month and year are present and day is missing:

- If year = year of the first dose and  
If month = month of the first dose then set day to day of first dose  
If month < month of first dose then set day to last day of month  
If month > month of first dose then set day to first day of month
- If year < year of first dose then set day to last day of month
- If year > year of first dose then set day to first day of month

For all other cases, set onset date to the first dose.

### **7.2.2 For Concomitant Medications and Procedures/Therapies Missing Dates**

Start Date:

- If (year is present and month and day are missing) or (year and day are present and month is missing) then set month and day to January 1.
- If year and month are present and day is missing then set day to first day of month.

End Date:

- If (year is present and month and day are missing) or (year and day are present and month is missing) then set month and day to December 31.
- If year and month are present and day is missing then set day to last day of the month.

## **8 STATISTICAL ANALYSIS**

### **8.1 General Aspects of the Statistical Analysis**

Treatments will be labeled as follows in data summaries for Part B:

- TSND-201
- Placebo

- Total (if needed)

### **8.1.1 General Rules**

Continuous variables will be summarized using the following descriptive summary statistics: the number of subjects (n), arithmetic mean, standard deviation (SD), standard error (SE), median, minimum value (Min), and maximum value (Max). The decimal places of Mean and Median will be formatted to one more than the original value. The decimal places of SD and SE will be formatted for two more than the original value. The decimal places of Min and Max will be formatted with the same as original value. The number of decimal places cannot exceed 4.

Frequencies (n) and percentage (%) will be used to summarize categorical data, and percentage is formatted for one decimal place. If the percentage is 0, then percentage is set to null. If the percentage is 100, then it is formatted as 100.0.

The derived data will reserve one more decimal place than the original. Descriptive statistics of derived data follow the above rules.

### **8.1.2 Software**

SAS 9.4 or higher is used for statistical analysis.

### **8.1.3 Definition of Baseline**

Baseline values will be defined as the worst measurement prior to the initiation of study treatment (or last non-missing if only one measurement was taken), unless specified otherwise for the corresponding endpoint.

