### 1.3 Schedule of Assessments (SoA)

	Screening		Treatment Period												Follow-Up Period					ET
Visit Number	1	2	3	4	5	6	7	8	9	10	11	12	13	14	15	16	17	18	19	-
Visit Session	ScrN	BL/ Prep	Treatment 1			Treatment 2			Treatment 3			Treatment 4			FU1	FU2	FU3	TC	FU4 /EOS	ET visit
Study Day(s)	-28 to BL	-4 to - 1	1	2	3 (+1)	8 (±1)	9	10 (+1)	15 (±1)	16	17 (+1)	22 (±1)	23	24 (+1)	29 (±1)	36 (±2)	43 (±2)	57 (±2)	64 (±3)	-
ICF	X																			
Demography	X																			
Confirm Eligibility	X	X	X																	
Med Hx	X																			
Substance Use Hx	X																			
Drug Use Assessment 	X	X	X			X	X		X			X								
Pregnancy Test 	X		X			X	X		X			X			X					X 
Physical Exam	X 														X				X 	X 
Vital Signs 	X	X	X 			X 			X 			X 			X					X 
12-Lead ECG	X		X 			X 			X 			X 			X					X 
Clinical Labs 	X								X						X					X 
MINI (central rater)	X																			
LEC-5	X																			
SPQ	X																			
SCID-5-PD (Central rater) 	X																			
CAPS-5 (past month; central rater)	X																			
C-SSRS 	X	X	X	X	X	X	X	X	X	X	X	X	X	X	X	X	X	X	X	X
Preparatory Session 		X																		
Randomization 			X																	
Study Drug Admin 			X			X			X			X								

 Urine drug screen must be confirmed as negative prior to enrollment and each dose. Site must confirm patient is not otherwise impaired prior to dosing.

 Urine test for WOCBP only. Pregnancy test must be confirmed as negative prior to enrollment and each dose. Serum FSH may be conducted at Screening to confirm non-childbearing potential.

 Only required if the ET visit occurs prior to the Day 29 visit.

 Height and weight will be collected at Screening; weight will be conducted at the end of study.

 Includes heart rate, blood pressure, and temperature.

 Vital signs during the dose session: BP and HR - predose, every 30-minutes post-initial dose, and prior to the booster dose; temperature- predose (within 10 min), and every 60 minutes.

 ECGs will be captured predose and at the end of the dosing session.

 Clinical labs will be assessed by a central lab.

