 C-SSRS should be conducted at any unscheduled visits.

 To be performed after all baseline assessments.

 Subjects enrolled in Part B only.

 Completed only if participant endorses a positive response to paranoid personality disorder, antisocial personality disorder, and borderline personality disorder on the SPQ.

Visit Number	Screening		Treatment Period												Follow-Up Period					ET
	1	2	3	4	5	6	7	8	9	10	11	12	13	14	15	16	17	18	19	-
Visit Session	Scrn	BL/ Prep	Treatment 1			Treatment 2			Treatment 3			Treatment 4			FU1	FU2	FU3	TC	FU4 /EOS	ET visit
Study Day(s)	-28 to BL	-4 to - 1	1	2	3 (+1)	8 (±1)	9	10 (+1)	15 (±1)	16	17 (+1)	22 (±1)	23	24 (+1)	29 (±1)	36 (±2)	43 (±2)	57 (±2)	64 (±3)	-
AEs			X	X	X	X	X	X	X	X	X	X	X	X	X	X	X	X	X	X
Con Meds	X	X	X	X	X	X	X	X	X	X	X	X	X	X	X	X	X	X	X	X
CAPS-5 (past-week; central rater)		X			X			X			X			X	X	X	X		X	X
MADRS (central rater)		X			X			X			X			X	X	X	X		X	X
CGI-S (central rater)		X			X			X			X			X	X	X	X		X	X
CGI-I (central rater)					X			X			X			X	X	X	X		X	X
PCL-5	X	X			X			X			X			X	X	X	X		X	X
BDI-II		X									X				X		X		X	X
SDS		X			X			X			X			X	X	X	X		X	X
WEMWBS		X									X				X		X		X	X
PGI-S		X			X			X			X			X	X	X	X		X	X
PGI-C					X			X			X			X	X	X	X		X	X
PSQI		X													X				X	X
PTGI		X													X				X	X
BIQ 															X					X
Reflection session															X	X	X			

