## 4.2 Study Visit Breakdown

Screening Period		
Study Visit	Visit Timing	Brief Description of Events
Screening (Visit 1)	Day -28 to Baseline	
Obtain informed consent and assess all Screening measures including Clinician Administered PTSD Scale for DSM-5 (CAPS-5; past month version), MINI 7.0.2, PCL-5, LEC-5, SPQ (and SCID-5-PD, if needed) C-SSRS, demographics and medical history, substance use history and pre-study medications.
 
The CAPS-5, MINI, and SCID-5-PD (if needed) will be administered by the Central rater and recorded for rater fidelity.
 
Physical examinations (including height and body weight), vital signs, temperature, 12-lead ECG, and labs (including safety labs, urine drugs test, and pregnancy test [women of childbearing potential (WOCBP) only, see Section 14.4], plus serum follicle stimulating hormone [FSH] test [if needed, see Section 14.4]) and a review of eligibility criteria will also be performed.

Baseline/Preparatory Session		
Study Visit	Visit Timing	Brief Description of Events
Baseline/Preparatory Session (Visit 2)	Day -4 to Day -1	
Baseline: The following safety assessments will be assessed prior to evaluations by the central rater to ensure the participant continues to meet eligibility requirements: urine drugs test, vital signs, concomitant medication review, and C-SSRS.
 
Central rater scales will be administered via telephone/video; the CAPS-5 will be performed first followed by MADRS and CGI-S. The CAPS-5, MADRS, and CGI-S will be recorded for rater fidelity.
 
This will be followed by the participant completing the self-administered psychometric assessments (PCL-5, BDI-II, SDS, WEMWBS, and PGI-S) as well as the PSQI and PTGI. The order of completion should be: Central rating scales and then the participant reported scales.
 
Preparatory Session: The following session is to be performed after all baseline assessments have been performed:
 
 
• Psychoeducation session, conducted by a trained dosing session monitor. The dosing session monitor will proactively provide the participant with an understanding of the anticipated experience following administration of an entactogen medication, like methylone.
 
 
If needed, a second preparatory session may occur prior to first dosing to ensure the participant is adequately prepared for the treatment period.

Treatment Period		

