### 6.1 Inclusion Criteria

1. Male or female participants aged between 18 to 65 years, inclusive.
2. Participant meets the DSM-5 criteria for current severe PTSD diagnosis, with a symptom duration of at least 6 months at Screening, as assessed by the following psychometric assessments:
  - a. CAPS-5 (past month version).
  - b. Life Events Checklist for DSM-5 (LEC-5).
    - The PTSD diagnosis will be confirmed at Baseline by the central rater.
3. Participant must have a CAPS-5 score of  $\geq 35$  at Screening and  $\geq 28$  at Baseline.
4. Participant has failed at least one treatment for PTSD (either psychotherapy or pharmacological treatment).
5. Proficient in reading and writing in local language sufficient to complete questionnaires.
6. Free from any other clinically significant illness or disease that may adversely affect:
  - a. the safety of the participant, or,
  - b. the integrity of the study (see [Section 6.2](#)).
7. Willing to refrain from taking any psychiatric medications or interventions during the study, unless provided by the Site Investigator.
  - No participant will be asked to discontinue potentially beneficial treatment in order to participate in this study.
8. Willing to provide a contact for emergencies.
9. Willing to be contacted via telephone for all necessary telephone contacts.
10. <Removed in Amendment 3>
11. Males who engage in sexual activity that has the risk of pregnancy must agree to use one of the following acceptable contraceptive methods and agree to not donate sperm throughout the study and for at least 90 days after the last dose of the study medication:
  - a. Use of a double barrier method (male condom with a diaphragm or a cervical cap)
  - b. Female use of hormonal contraceptives (as described below)
  - c. Either partner is surgically sterilized (as described below)
  - d. Abstinence, if consistent with the participants preferred and usual lifestyle

12. Females of childbearing potential\* who are sexually active with a male partner must be willing to use one of the following acceptable contraceptive methods throughout the study and for at least 1 month after the last study drug administration.
  - a. Hormonal contraceptives or intrauterine devices: at least 4 weeks before first dosing and must follow that product's package insert instructions including additional protection at times when hormonal contraceptive doses might be missed

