### **8.1 Clinician-Administered Psychometric Assessments**

#### **8.1.1 Clinician-Administered PTSD Scale for DSM-5 (CAPS-5)**

The CAPS-5 is a 30-item structured interview that can be used to:

- Make current diagnosis of PTSD.
- Assess change in PTSD symptoms over time.

In addition to assessing the 20 DSM-5 PTSD symptoms, questions target the onset and duration of symptoms, subjective distress, impact of symptoms on social and occupational functioning, improvement in symptoms since a previous CAPS administration, overall response validity, overall PTSD severity and specifications for the dissociative subtype (depersonalization and derealization). The CAPS-5 also rates intrusion symptoms (intrusive thoughts or memories), avoidance, cognitive and mood symptoms, arousal and reactivity symptoms, duration and degree of distress. For each symptom, standardized questions and probes will be provided.

The ‘past month’ version of the CAPS-5 will be performed at Screening. The ‘past week’ version of the CAPS-5 will be performed at each subsequent study visit. The participant will report on the same Criterion A event specified at Screening for all CAPS-5 assessment timepoints.

Each CAPS-5 will be administered by a central rater via telephone or video call.

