## 3 STUDY DESIGN

### 3.1 Study Design Overview

This is a two-part study to assess methylone for the management of the symptoms of PTSD. Part A was an open-label, non-controlled assessment in approximately 15 evaluable participants with PTSD to assess early safety and efficacy and to confirm procedures included in the blinded portion (Part B) of the study. After completion of Part A, enrollment for Part B began. Unless otherwise stated, Part B is identical to Part A with the exception of the inclusion of a placebo arm in Part B. This SAP covers the analysis of the Part B data.

Part B is a randomized, double-blind, parallel-group, placebo-controlled assessment of methylone for the management of the symptoms of PTSD in approximately 64 patients. This multi-center study will be conducted in up to 25 sites globally.

There are 4 planned dose sessions for each participant. Participants in Part B will be randomized 1:1 to the one of the two study treatment arms and will receive treatment at each of the weekly dose sessions for the duration of the study.

The two blinded study treatment arms for Part B are:

- Methylone 150 mg, with a booster administration of 100 mg administered 90 ( $\pm$ 10) minutes after the initial administration, during each dose session.
- Matched placebo at each timepoint (initial + booster) during each dose session.

For each participant the study consists of:

- **Screening Period (Day -28 to Baseline):** Informed consent, eligibility assessment, and enrolment of eligible participants.
- **Baseline/Preparatory Session (Day -4 to Day -1):** Baseline assessments, confirmation of eligibility, and a preparatory psychoeducation session leading to enrolment confirmation.
- **Treatment Period (Day 1 to Day 24):** Four weekly dose sessions. Each dose session is followed by a safety phone call 1 day after dosing and efficacy assessments 2 days after dosing.
- **Follow-Up Period (Day 29 to Day 64):** Follow-Up visits for efficacy and safety will occur at 1, 2, 3 and 6 weeks post-final study drug administration..

The expected duration of participation for each participant who completes all study visits, from Screening to the EOS visit, is up to 16 weeks.

Screening (Up to 28 days)		Treatment Period (4 weeks) (methylone [Part A]; methylone or placebo [Part B])												Follow-up (6 Weeks)				
Day -28 to Baseline		Treatment #1			Treatment #2			Treatment #3			Treatment #4			Day 29	Day 36	Day 43	Day 57	Day 64

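### SAP 8.1.3 takes the worst pre-treatment score as baseline, so CAPS-5 and PCL-5 change would be counted from the higher of two pre-dose scores

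*SAP*

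**What the plan says.** SAP 8.1.3 sets the general rule: "Baseline values will be defined as the worst measurement prior to the initiation of study treatment". It falls back on the last available value where only one measurement exists, and it lets an endpoint set its own baseline. Two sections do so: SAP 8.4.3 (vital signs, Visit 2 per participant) and SAP 8.4.4 (ECG, Visit 1 per participant). The CAPS-5 scoring text (SAP 6.1.1), the MMRM section (8.3.1.1), the primary endpoint (8.3.2.1) and the response definitions (8.3.2.2.1) name neither a baseline visit nor a CAPS-5 version.

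Two CAPS-5 interviews precede dosing. The Protocol's Schedule of Assessments has one row, "CAPS-5 (past month; central rater", marked at Screening only. A second row, "CAPS-5 (past-week; central rater", is marked at Visit 2 and at the later efficacy visits. Protocol 8.1.1 agrees: the past-month "version of the CAPS-5 will be performed at Screening", and the past-week version is used from then on. Inclusion criterion 3 ("Participant must have a CAPS-5 score of") sets separate floors of 35 at Screening and 28 at Baseline.

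PCL-5 is also taken twice. Protocol 4.2 lists it at Screening ("past month version), MINI 7.0.2, PCL-5, LEC-5, SPQ") and again at Visit 2 ("self-administered psychometric assessments (PCL-5, BDI-II, SDS, WEMWBS, and PGI-S"). SAP 6.1.5 gives it a past-week recall throughout.

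**The concern.** Higher CAPS-5 scores are worse, so the rule as written makes the baseline the maximum of the Screening and Visit 2 scores. Two things follow. A past-month score can become the reference for past-week follow-up scores. And choosing the higher of two noisy readings builds in regression to the mean, so a fall that happened before any drug was given is reported as change after treatment, in both arms.

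The results exposed are mean CAPS-5 change by arm and the 10-point, 30% and 50% response rates, which are Part B secondary endpoints. SAP 8.1.5 says the findings will be used to design and power later trials, and SAP 9 says the analyses may go into submissions or manuscripts. Inflated placebo change and response rates are poor planning inputs. They would also be hard to compare with trials that measure change from a single baseline visit.

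**Working it through.** **The plan's own figures.** No stated figure depends on the baseline rule. The effect and SD used below (11 points, SD 12, SAP 4) reproduce the stated evaluable numbers: two-sided t-test power at 0.05 is 80.6% with 20 per arm and 91.1% with 27.

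**Direction (exact).** Let S be Screening, V the Visit 2 score, Y a later score (Y ≥ 0) and B = max(S, V). Since B ≥ V:

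- B − Y ≥ V − Y, so improvement is never smaller.
- 1 − Y/B ≥ 1 − Y/V, so percentage improvement is never smaller.

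A check of every integer combination allowed by the entry floors (S 35–80, V 28–80, Y 0–80; 46 × 53 × 81 = 197,478) found no smaller improvement and no lost response.

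**Size at the entry floors (exact), with no change after dosing.**

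| Screening | Visit 2 | Week 10 | Change from Visit 2 | Change under the literal rule |
|---|---|---|---|---|
| 35 | 28 | 28 | 0 | 35 − 28 = 7 points; 7/35 = 20% |
| 38 | 28 | 28 | 0 | 38 − 28 = 10 points: 10-point responder |
| 40 | 28 | 28 | 0 | 40 − 28 = 12 points; 12/40 = 30%: meets the 10-point and 30% definitions |

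For a participant at 35 then 28, the later score needed for response moves from 18 to 25 (10 points), from 0.7 × 28 = 19.6 to 0.7 × 35 = 24.5 (30%), and from 14 to 17.5 (50%).

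**Size in a trial population (simulated).** The documents do not say how often Screening exceeds Visit 2.

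- *From the documents:* effect 11, SD 12, mean 47.8 (the Part A baseline, Protocol 2.4.1), and the entry floors.
- *Assumed:* visit SD 7 or 9; Screening–Visit 2 correlation 0.5 to 0.9; Screening mean 0 or 5 points above Visit 2; mean change from Visit 2 to Week 10 of −8 on placebo, hence −8 − 11 = −19 on methylone.
- *Model A:* Week 10 = Visit 2 + N(mean change, 12).
- *Model B:* Week 10 is a third noisy reading of the same underlying severity, scaled so that change from Visit 2 has SD 12.

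Ranges cover both models, with 500,000 draws per scenario:

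| Quantity | Visit 2 baseline | Literal rule, no mean fall | Literal rule, 5-point mean fall |
|---|---|---|---|
| Inflation of within-arm improvement (points) | – | 1.3–3.7 | 5.1–6.6 |
| Participants with Screening ≥10 above Visit 2 | – | 0.1–15% | 8–31% |
| Placebo 10-point response | about 45% | 49–58% | 61–68% |
| Methylone 10-point response | 78–79% | 81–88% | 88–92% |
| 10-point arm difference (percentage points) | 33–34 | 28–32 | 24–27 |

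Across all scenarios the arm difference moves by −4.0 to +0.5 percentage points for 30% response and by +0.9 to +6.3 for 50% response. The baseline-adjusted Week 10 mean difference, a single-visit stand-in for the MMRM, moves by 0.03 points or less. Residual SD rises 1–13% under model A and falls 0.1–1.3% under model B.

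A separate simulation with other assumptions (mean 45, SD 8, pre-dose fall 0 or 3, correlation 0.5–0.9) gave inflation of 1.5–5.0 points. The 10-point response rate rose by about 5–15 percentage points in a placebo-like arm and 2–7 in an active-like arm. The adjusted difference was again stable (for example −10.73 against −10.70).

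**The case against.** **Visit 2 was surely meant.** Protocol 4.2 and SAP 3.1 both call that visit Baseline; SAP 3.1 describes it as "Baseline assessments, confirmation of eligibility, and a preparatory psychoeducation session leading to enrolment confirmation". SAP 8.2.3.2 names the Screening CAPS-5 explicitly when it wants it. SAP 1 says methods follow the Protocol unless a departure is stated, and SAP 9.1 lists no change of baseline. Protocol Table 1 specifies a one-week CAPS-5 score for Part A, and Part B is described as identical apart from placebo. If the two versions count as different measures, only one past-week value exists before dosing, and the rule's own single-measurement clause leads to Visit 2. This is good evidence of intent, but it remains inference. Table 2 omits the one-week wording for Part B, SAP 6.1.1 does not separate the versions, and the SAP did think it necessary to name Visit 2 for vital signs. The argument also cannot help PCL-5, which is past-week at both visits.

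**The primary result is safe and the trial is not confirmatory.** The first part stands for the treatment contrast: the rule is the same in both arms and baseline is a covariate. Planning a later trial on the adjusted CAPS-5 difference would be little affected. Within-arm change and the responder results remain affected.

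**The sizes rest on assumptions.** They do, and the documents do not supply the inputs. Only the direction and the entry-floor examples are exact. The larger residual-SD increases come from model A, which builds Week 10 from Visit 2 and so penalises any other baseline. No loss of precision is established.

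**The table shells may settle it.** They are in a separate file that was not available. The governing definition still belongs in the SAP text.

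**Conclusion.** The concern holds and should be fixed. As written, the SAP's only general baseline rule selects the higher pre-dose CAPS-5 and PCL-5 score, and no efficacy section overrides it. Observed within-arm improvement and response rates can then only stay the same or rise; that follows from the arithmetic and needs no assumption.

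Under the assumed SDs, correlations and pre-dose falls, CAPS-5 improvement is inflated by 1.3 to 6.6 points. Placebo 10-point response gains roughly 4 to 23 percentage points (45% to 49–68%). Varying the Visit 2 mean (38 or 42) or the placebo change (−4 or −14) gives a similar rise of 4 to 22 points.

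The rule does not simply favour the drug. The 10-point arm difference tends to narrow, the 50% difference tends to widen, remission (11 or less) is unaffected, and the adjusted primary contrast is essentially unbiased. PCL-5 has no responder definition, so there the effect is mainly on reported within-arm change.

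**What to change.** In SAP 8.1.3, state that the baseline for all efficacy scales is the last non-missing Visit 2 value before first dose, using the past-week version for CAPS-5, and that Screening CAPS-5 and Screening PCL-5 are not used to derive it. Apply this one baseline to change scores, the MMRM covariate and every response definition. Limit any worst-value rule to safety variables listed by name.

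The cost is one or two sentences and no new data, since Visit 2 scores are already collected. There are two small consequences. Reported within-arm changes and response rates will look somewhat less favourable than under the literal rule. And because SAP 7.1 voids a total with any missing item and does not impute, a participant with an incomplete Visit 2 PCL-5 would have no PCL-5 baseline; the SAP should acknowledge this.
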